### **14.2 Peer review**

The study has been subject to expert peer review within the sponsor organisation. The review has been undertaken by a member of the organisation who is independent of the research team and independent of the financial team. The review indicates that the aims and objectives are achievable based upon the design and methodology.

### **14.3 Public and patient involvement**

Sponsor recognises the value of patient and public involvement, and therefore service users have been involved in the design of the research, to review and improve the protocol design and participant information sheet design. This involvement was kindly facilitated by NIHR MindTech Healthcare Technology Co-operative.

### **14.4 Protocol compliance**

Prospective, planned deviations or waivers to the protocol are not allowed. Accidental protocol deviations can happen, and the research nurse should adequately document these and report to the CI and sponsor legal representative immediately.

Deviations from the protocol which are found to frequently recur are not acceptable, will require immediate action and could potentially be classified as a serious breach.

### **14.5 Notification of serious breaches to GCP and/or the protocol**

A serious breach is a breach which is likely to effect to a significant degree:

- The safety or physical or mental integrity of the participants
- The scientific value of the study

The CI and sponsor legal representative will be notified immediately of any case where the above definition applies during the study, and immediate action will be undertaken.

#### **14.6 Data protection and patient confidentiality**

All investigators and host site staff must comply with the requirements of the Data Protection Act 1998 with regards to the collection, storage, processing and disclosure of personal information and will uphold the Act's core principles.

Participants will be assigned a coded, depersonalised study ID upon consent. The study ID will be used on all documentation emailed to the sponsor. The sponsor will never receive personally identifiable data. The linking document between the code and the participant's identifying information will be retained at the host site. The custodian of the data remains the Caldicott Guardian within Nottinghamshire Healthcare NHS Foundation Trust.

#### **14.7 Financial and other competing interests**

Host site (Nottinghamshire Healthcare NHS Foundation Trust) will receive payment for enrollment of participants in the study, in accordance with the negotiated fee outlined in the NIHR CRN Industry Costing Template.

Neither the CI, PI nor host site staff have any commercial ties to the Sponsor nor Sponsor's Legal Representative.

#### **14.8 Indemnity**

Sponsor has sufficient indemnity in place for the management and design of the study, and NHS indemnity will be in place for the conduct of the study at the host site.

#### **14.9 Amendments**

Amendments will be notified to the HRA, REC and host site as per requirements under UK procedures.

16 APPENDIX A: GAD-7

Over the last 2 weeks, how often have you been bothered by any of the following problems?

	Not at all	Several days	More than half the days	Nearly every day
1 Feeling nervous, anxious or on edge	0	1	2	3
2 Not being able to stop or control worrying	0	1	2	3
3 Worrying too much about different things	0	1	2	3
4 Trouble relaxing	0	1	2	3
5 Being so restless that it is hard to sit still	0	1	2	3
6 Becoming easily annoyed or irritable	0	1	2	3
7 Feeling afraid as if something awful might happen	0	1	2	3

GAD7 total score

(Data item 38 in the IAPT Data Standard)

17 APPENDIX B: CSRI

**Ethnicity**

Indicate participant's ethnicity, by marking with a cross (X) in the relevant box.

White		
1	English/Welsh/Scottish/Northern Irish/British	
2	Irish	
3	Gypsy or Irish traveler	
4	Any other White background, please describe:	
Mixed/multiple ethnic groups		
5	White and Black Caribbean	
6	White and Black African	
7	White and Asian	
8	Any other Mixed/multiple ethnic background, please describe:	
Other Ethnic group		
9	Arab	
10	Any other Ethnic group, please describe:	
Asian/British		
11	Indian	
12	Pakistani	
13	Bangladeshi	
14	Chinese	
15	Any other Asian background, please describe:	
Black/African/Caribbean/Black British		
16	Black Caribbean	
17	Black African	
18	Black other	
19	Any other Black/African/Caribbean background, please describe:	

**Highest qualification**

Indicate participant's highest qualification, by marking with a cross (X) in the relevant box.

1	Higher degree	
2	First degree	

3	Other higher qualification	
4	A-level	
5	O-level / GCSE	
6	Other qualification	
7	No qualification	

### Marital status

Indicate participant's marital status, by marking with a cross (X) in the relevant box.

1	Married	
2	Single	
3	Partner	
4	Divorced	
5	Widowed	

### Occupational status

Indicate participant's occupational status, by marking with a cross (X) in the relevant box.

1	Employed	
2	Self-employed	
3	Voluntary employment	
4	Student / training	
5	House wife / husband	
6	Unemployed	
7	Retired	

Indicate participant's number of hours worked each week, in hours and minutes.

Number of hours worked each week (XX:XX)	
--	--

If participant is employed, indicate the participant's occupational group, by marking with a cross (X) in the relevant box.

1	Manager / administrator	
2	Professional (eg, health, teaching, legal)	
3	Clerical worker / secretary	
4	Services / sales	
5	Skilled labour / craftsmen (eg, building, electrical)	
6	Factory worker	
7	Other, please specify:	

### Costs

The following questions relate to the various costs associated with participant health care to do with participant health problems. Where the participant is unsure of exact numbers, please ask participant to provide best estimate or average.

### Monthly net income

Indicate participant's monthly net income, by marking with a cross (X) in the relevant box.

1	£0.00 - £500.00	
2	£500.00 - £1000.00	
3	£1000.00 +	

Indicate duration of time participant has taken off work because of ill-health in the last 3 months, by indicating numerical values in each box.

1	Months (XX)	
2	Weeks (XX)	
3	Days (XX)	

If participant is unemployed, indicate the primary reason, by marking with a cross (X) in the relevant box.

1	Mental illness	
2	Physical disability	
3	General employment situation	
4	Redundancy	
5	Other, please specify:	

If participant receives social security benefits, indicate by marking with a cross (X) in the relevant box.

	Yes	No
Participant receives social security benefits		

If participant does receive social security benefits, indicate which by marking with a cross (X) in the relevant box(es).

1	Income support	
2	Incapacity benefit (pre January 2011 / ESA (post January 2011))	
3	Jobseekers allowance (previously unemployment benefit)	
4	Statutory sick pay	
5	Housing benefit	
6	Severe disablement allowance	
7	Mobility allowance	
8	Family (child tax) credit	
9	Lone parent benefit	

10	Attendance allowance	
11	Other, please specify:	

Indicate participant's total amount of benefit received each week.

Total amount of benefit received per week (£XX.XX)	
--	--

Indicate participant's main source of income, by marking with a cross (X) in the relevant box.

1	Salary / wage	
2	State benefits	
3	Pension	
4	Family support (ie, from spouse)	
5	Other, please specify:	

### Use of outpatient hospital services over the last 3 months

Indicate yes or no, by marking with a cross (X) in the relevant box.

	Yes	No
Participant has made any outpatient hospital visits in the last 3 months		

If yes, provide further detail below.

	Service	Total number of appointments in last 3 months
1	Accident and Emergency department	
2	Radiology department	
3	Physiotherapist	
4	Occupational Therapist	
5	Psychiatric outpatient visit	
6	Other, please specify:	

### Use of inpatient hospital services over the last 3 months

Indicate yes or no, by marking with a cross (X) in the relevant box.

	Yes	No
Participant has made any inpatient hospital visits in the last 3 months		

If yes, provide further detail below.

	Service	Total number of admissions in last 3 months	Total number of inpatient days
1	General medical ward		
2	Psychiatric rehabilitation ward		
3	Acute psychiatric ward		
4	Other, please specify:		

#### Any primary and community care contacts over the last 3 months

Indicate yes or no, by marking with a cross (X) in the relevant box.

	Yes	No
Participant has used any primary and community care services in the last 3 months		

If yes, provide further detail below.

	Service	Total number of contacts in last 3 months	Average duration of each attendance (minutes)
1	GP surgery		
2	GP home visit		
3	Practice nurse		
4	Community psychiatric nurse		
5	Walk-in centre		
6	Out-of-hours care		
7	Occupational therapist		
8	Social worker		

9	Advocate (eg, creative support)		
10	Home-help / home care worker		
11	Community support worker		
12	Psychiatrist		
13	Psychologist		
14	Other, please specify:		

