#### 3.5 Secondary outcome measures

The secondary objective will be measured using the Client Service Receipt Inventory (CSRI), adapted for use for anxiety disorders in primary care and community settings, which is a measure of the full health and social care cost and patient cost of treatment. Additionally, the objective will be measured using the EQ-5D-5L, which is a participant-reported measure of health utility and quality of life used by NICE to generate QALYs for cost effectiveness assessments, and uses 6 items. Finally, the objective will be measured using the Work and Social Adjustment Scale (WASA) which is a participant-reported measure of work and social function, and uses 8 items.

- The outcome measure for **CSRQ** is the change in cost impact for previous 12 weeks from baseline to week 24.
- The outcome measure for **EQ-5D-5L** is the change for participants from baseline to week 24.
- The outcome measure for **WASA** is the change for participants from baseline to week 24.

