## **8.2 End of study provision**

The device is marketed and sold in the UK by the sponsor legal representative, and are available from private purchase at a cost of £499.00. Participants will be fully informed that participation in the study will result in a maximum of 12 weeks of Alpha-Stim AID device treatment, after which time point the device must be returned to the research nurse. Participants will not be encouraged to purchase a device, but will be advised by the research nurse if an interest is expressed. Participants will not receive a discount on the purchase of a device.

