## **11 STATISTICS AND DATA ANALYSIS**

### **11.1 Sample size calculation**

If Alpha-Stim AID CES has a comparable effect to IAPT high intensity psychological therapy interventions in patients with a primary working diagnosis of GAD, it will achieve an effect size of 1.04 (95% CI 0.88 to 1.23) in an intention to treat sample of 4,183 participants with pre-treatment GAD-7 score of 14.06 (s.d. 5.11) and post treatment GAD-7 score of 8.10 (s.d. 6.37) (Richards and Borglin, 2011). Reliable improvement was obtained after IAPT treatment for generalised anxiety disorder in 54.7%, reliable improvement plus clinically significant change in 40.1% and recovery in 46.0%.

However, to make a meaningful economic impact on NHS care, then Alpha-Stim AID CES does not need to be as effective as IAPT high intensity psychological therapy interventions. In a previous randomised controlled trial (Barclay and Barclay 2014), Alpha Stim CES reduced the mean Hamilton Anxiety score from 29.5 to 13.4 while sham Alpha Stim CES reduced it from 27.6 to 20.0 over 5 weeks  $p=0.001$ ,  $d=0.94$ , with 83% patients showing a drop of 50% in HAM-A score.

A meta-analysis of 14 Alpha Stim CES randomised controlled trials estimates an average effect size of 0.60. On this basis reliable improvement may be seen in 33%, reliable improvement plus clinically significant change in 24% and recovery in 28% cases.

The cost of IAPT high intensity psychological therapy intervention is estimated to be £2,895.00 per participant and £2,914.00 if stepped care was involved (Radhakrishnan et al, 2013). On a cost offset basis if Alpha-Stim AID CES cost £465.00, then reliable improvement plus clinically significant change (which would not necessitate high intensity treatment) in only 20% would be clinically and cost effective.

Taking all data into account, 60 patients would be required to complete Alpha Stim AID CES treatment and all assessments. However, to allow for drop-out from assessments, drop-out from Alpha-Stim AID CES, and choice in relation to IAPT high intensity psychological therapy intervention ,120 patients will be recruited.

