It is anticipated from a sample size of 120, then at least 40 (33%) would show reliable improvement, 29 (24%) plus clinically significant improvement, and 34 (28%) recovery at 6 months. Since a repeat course of Alpha-Stim from 6 to 12 weeks can result in further improvement in those who have made some improvement in symptoms, we estimate that a further 20 (17%) will make a reliable improvement in their symptoms. Therefore, it is anticipated that 60 (50%) will make a reliable improvement in their GAD-7 symptoms requiring no additional psychological treatment or a minimal psychological treatment intervention (in those with other symptoms or do not make a reliable improvement plus clinically significant change).

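### No CSRI row names, and no scheduled item counts, IAPT high intensity sessions, so the cost outcome can under-record the very cost whose avoidance is the economic case

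*Combined protocol and SAP*

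**What the plan says.** Section 3.5 makes the CSRI the main cost measure, "which is a measure of the full health and social care cost and patient cost of treatment", and defines the outcome as the change between the 12 weeks before baseline and the 12 weeks before week 24.

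Section 11.1 gives the economic case: "The cost of IAPT high intensity psychological therapy intervention is estimated to be £2,895.00 per participant and £2,914.00 if stepped care was involved". It continues, "On a cost offset basis if Alpha-Stim AID CES cost £465.00", with a 20% share of patients who respond well enough not to need that therapy judged sufficient. It then forecasts that 60 of 120 participants will improve reliably on the GAD-7, "requiring no additional psychological treatment or a minimal psychological treatment intervention".

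In Appendix B, the community section opens with "Participant has used any primary and community care services in the last 3 months" and gives 13 named services plus an open row. The outpatient section gives five named services plus an open row. The private therapy item under *Other costs* does not reach NHS sessions.

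The visit lists in section 7.5 and the table in section 7.6 cover the scales, the CSRI, compliance and adverse events. Section 12.1 names only the GAD-7, WASA and PHQ-9 as already set up in PCMIS. Section 12.2 describes access to records for monitoring and audit.

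**The concern.** The quantity that decides the economic question is how much high intensity therapy participants go on to receive. Sections 4 and 7.1 name the providers as PWPs and Cognitive Behavioural Therapists, but neither appears on the CSRI, and neither does a step three assessment or a CBT session. A session is counted only if the participant mentions it and the nurse chooses a row for it. Once entered, it may sit alongside unrelated psychologist contacts.

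Two things are at stake. The cost outcome, offered as complete, may under-record the largest cost that the documents quantify. And the part of the section 11.1 forecast about needing little or no further therapy has no reliable data behind it. Section 2 says the study is meant to supply NICE with an assessment of economic impact, so this gap touches its main purpose.

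**Working it through.** **1. Where a step three session could be entered**

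| Place | Named IAPT, CBT or PWP item? | Possible entry |
|---|---|---|
| Visit lists (7.5) and table (7.6) | No | None apart from the CSRI |
| CSRI outpatient, 5 named rows | No | Open row 6 |
| CSRI inpatient, 3 named wards | No | Not applicable |
| CSRI community, 13 named rows | No | *Psychologist* (row 13) or open row 14 |
| CSRI private therapy item | No | Private sessions only |
| PCMIS (12.1) | No session extract planned | None |

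Rows 13 and 14 collect the number of contacts and their average duration over three months. Capture is therefore possible, but it is unprompted and undifferentiated.

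**2. The plan's own figures** (therapy £2,895 or £2,914 and device £465 from 11.1; device price £499 from 8.2)

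- Offset at 20% avoidance: 0.20 × 2,895 = £579. Net of the device: 579 − 465 = £114, or 579 − 499 = £80. So 20% is sufficient, as the plan says.
- Break-even share: 465 / 2,895 = 16.1%. The other pairings give 465 / 2,914 = 16.0%, 499 / 2,895 = 17.2% and 499 / 2,914 = 17.1%.
- Forecast: 40 + 20 = 60, and 60 / 120 = 50%.
- Relative size: 2,895 / 465 = 6.2. The only other unit cost of care given is the drug in section 1, at £80 per 28 days, or 6 × 80 = £480 over 24 weeks.

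**3. Upper bound on the error.** Assume each affected participant has a full £2,895 course, wholly unrecorded and wholly inside the look-back.

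- Per 10 percentage points missed: 0.10 × 2,895 = £289.50, and 289.50 / 465 = 62%.
- Share missed that equals the device cost: 465 / 2,895 = 16.1%.

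**4. Range over assumed capture.** Suppose 20% avoid therapy and the rest have a full course. Mean cost of device plus therapy is 465 + 0.80 × 2,895 = £2,781.

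| Share of therapy cost captured | Recorded mean | Missed per participant |
|---|---|---|
| 100% | £2,781 | £0 |
| 75% | £2,202 | £579 |
| 50% | £1,623 | £1,158 |
| 0% | £465 | £2,316 |

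At 75% capture the missed £579 is as large as the gross offset in step 2. If 50% avoid therapy, the mean is 465 + 0.50 × 2,895 = £1,912.50, and 75%, 50% and 0% capture miss £361.88, £723.75 and £1,447.50.

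**5. Direction.** Let H be step three cost in the 12 weeks before week 24, S be step two cost in the 12 weeks before baseline, and u and v the shares of each left unrecorded. Participants are waiting for step three at baseline, so its cost there is essentially nil. Then:

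recorded change = true change − uH + vS

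The first term flatters the device and the second works against it. Section 1 calls step two relatively inexpensive, so the balance probably favours the device, but the documents do not give S.

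**6. Timing.** Section 7 allows therapy to start after a minimum wait of 6 to 8 weeks. Sessions before about week 12 fall outside the section 3.5 comparison even if recorded. The flow chart puts the CSRI at week 6, whereas sections 7.5 and 7.6 put it at week 12. Under the flow chart, roughly weeks 6 to 11 fall in no three-month recall window.

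**The case against.** The strongest reply is that the CSRI is not blind to these contacts. The *Psychologist* and *Other* rows can hold them, the questionnaire is administered by a nurse, and those delivering the study know that participants are awaiting step three. That stands. A reader might infer that CBT sessions cannot be recorded at all, and the documents do not support that. The defect is unreliable capture that does not distinguish step three.

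A reader might also infer that missing CBT could by itself produce a reported fall in cost. It cannot. With step three cost near nil before baseline, and other costs and step two recording held constant, the true change is H and the recorded change is (1 − u)H, which is never negative. Under-recording can hide a rise, or enlarge an apparent net saving against a benchmark such as £2,895. Any actual fall must come from other services.

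Three further limits stand. The £290 is a maximum, because section 1 describes the minimum course as an assessment and two sessions, and the documents do not say that £2,895 will be the unit cost applied. Therapy is the largest cost only among those quantified, as inpatient days are collected without a unit cost. And the GAD-7 part of the forecast can be checked, since that scale is taken at every visit.

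**Conclusion.** The concern holds as one of unreliable, undifferentiated capture. No CSRI row names, and no scheduled item counts, the therapy whose avoidance is the economic case, and no record extract fills the gap. The cost outcome can therefore under-record the largest cost the documents quantify, probably in the device's favour.

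The bound of about £290 per 10 percentage points of participants missed, with the device cost reached at about 16%, rests on full courses being wholly missed and lying inside the look-back. Shorter therapy, partial recording or earlier sessions would shrink it. The documents give no figure for the share missed. The therapy-need part of the section 11.1 forecast cannot be reliably checked. This should be corrected, but it does not affect the GAD-7 outcomes.

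**What to change.** - Add CSRI rows for the step three assessment, individual CBT sessions and PWP contacts.
- At the existing week 12 and week 24 visits, have the research nurse record the number and dates of IAPT sessions from PCMIS where it holds them, and otherwise by prompted recall. Together the two visits should cover weeks 0 to 24. Reconcile the flow chart with sections 7.5 and 7.6 on when the CSRI is given.
- Name this source in section 12.1, and confirm that consent covers it, since section 12.2 describes record access for monitoring and audit.
- Include these contacts in the cost outcome. State whether that outcome covers all 24 weeks or only the last 12.
- Report descriptively the number of high intensity sessions received by week 24. Do not claim that therapy was avoided, because there is no comparator.

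The cost is a few CRF fields, a few minutes at each of two visits already planned, and a check of the consent wording. No treatment or visit changes. Whether PCMIS holds session counts and dates in usable form is not stated and needs confirming with the site.

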### Travel costs

Indicate yes or no, by marking with a cross (X) in the relevant box.

	Yes	No
Participant has incurred any travel costs associated with use of services in the last 3 months		

If yes, provide further detail below.

Location	Main method of travel (eg, private car, bus)	Cost of return trip if public transport (£XX.XX)	Number of miles round trip if private car (XX.X)	Total parking fees (£XX.XX)
1				
2				
3				
4				
5				
6				

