- Step two: Upon failure to improve as a result of step one treatment, the patient will be referred by a GP to an Improving Access to Psychological Therapies (IAPT) service. Alternatively, a patient may self-refer directly to an IAPT service without having undertaken step one treatment in primary care. Upon referral or self-referral, all patients will receive an assessment to diagnose their problem. If indicated, patients will receive step two treatment - the basis of step two is low intensity psychological therapy intervention, which includes individual non-facilitated self-help, individual guided self-help and psychoeducation groups. Patients are assessed throughout step two.
- Step three: Upon failure to improve as a result of step two treatments, patients will be indicated to receive from the IAPT service, as a minimum, an assessment and two individual Cognitive Behavioural Therapy (CBT) treatment sessions focussed on long-term coping strategies. Dependent upon improvement, patients will receive further CBT sessions and support as required. Pharmacological treatment, initially with selective serotonin re-uptake inhibitor anti-depressants, and subsequently drugs such as pregabalin, may be prescribed by the GP independently of the IAPT service, for which pharmacological treatment are not part of the care pathway.

Step one and two treatment are relatively inexpensive, but are often ineffective. Step three treatment, both psychological and pharmacological, are relatively expensive, requiring frequent contacts with highly qualified health professionals within the IAPT service, and prescription of expensive drugs in primary care (for example, a 28-day treatment course of pregabalin is approximately £80.00). GAD is a relatively persistent clinical problem and therefore pharmacological treatment can extend for many months and years, whilst there are frequently substantial delays in offering access to high intensity psychological treatment intervention.

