### Other costs

Indicate yes or no, by marking with a cross (X) in the relevant box.

	Yes	No
Participant has purchased any over-the-counter medicines or attended any private therapy sessions as a result of symptoms during the last 3 months (including herbal or complementary remedies (eg, crystals and visits to alternative practitioners)		

If yes, provide further detail below.

Medicine / preparation / herbal remedy bought or appointment with private practitioner	Total number of purchases or visits in last 3 months	Cost of each remedy or private session
1		
2		
3		
4		
5		
6		
7		

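### The CSRI travel table records the fare or mileage of one return trip but not the number of trips, so three-month fares and mileage can only be approximated

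*Combined protocol and SAP*

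**What the plan says.** Section 3.2 sets the secondary objective as cost effectiveness in terms of service cost and patient cost. Section 3.5 makes the CSRI outcome the change in cost over the preceding 12 weeks from baseline to week 24. The schedule in section 7.6 places the CSRI at day 1, week 12 and week 24.

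In Appendix B, the travel block opens with a yes/no question: "Participant has incurred any travel costs associated with use of services in the last 3 months". If the answer is yes, a table of six blank rows follows with five columns: a free-text location, the means of transport, "Cost of return trip if public transport (£XX.XX", "Number of miles round trip if private car (XX.X" and "Total parking fees (£XX.XX". None of these is a number of trips. The header and the blank rows have the same number of cells, so nothing suggests that a column was lost when the text was read from PDF.

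The neighbouring tables are built differently. Other costs has a count, "Total number of purchases or visits in last 3 months", beside a cost per item or session. Additional care costs has a count of visits beside an average cost per visit.

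**The concern.** Fares and mileage are entered per journey, while the screening question and the outcome both refer to about three months. A per-journey cost becomes a three-month cost only when it is multiplied by a number of journeys, and the table does not collect that number. Travel is the only unit-cost table in the form without its own multiplier.

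At stake is one element of patient cost in an economic evaluation that section 2 says is meant chiefly for NICE and NHS England. The number of journeys is also the part most likely to move during the study. Participants start on a waiting list and may begin step-three therapy once the minimum 6 to 8 week wait has passed (section 7). Section 1 describes that therapy as "as a minimum, an assessment and two individual Cognitive Behavioural Therapy (CBT) treatment sessions", with more sessions as needed.

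**Working it through.** The plan states no travel-cost total, so there is no figure to reproduce. The check is whether the quantities needed are collected.

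**Formula.** Travel cost over three months = sum over locations of (n × u) + parking. Here n is the number of return trips and u is the return fare, or round-trip miles × a mileage rate.

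**What the form and plan supply.**
- Fare or miles per return trip: yes, in Travel costs.
- Parking: headed as a total. The column states no period; only the screening question does.
- n: not in the travel table.
- Mileage rate for costing: not stated. Section 7.3 gives £0.45 per mile, but only for reimbursing the baseline visit. Section 11.3 promises means and standard deviations by visit and gives no costing rule.

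**Step 1: one entry fits many totals.** Assume a 10-mile round trip and borrow £0.45 per mile for illustration: u = 10 × £0.45 = £4.50.
- 1 trip: £4.50
- 6 trips: 6 × £4.50 = £27.00
- 12 trips: 12 × £4.50 = £54.00

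The fare and mileage cells are identical in all three cases. The trip numbers are assumptions.

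**Step 2: the change from baseline.** For the same venue and means of transport, the true change in fares or mileage is (n at week 24 − n at baseline) × u. With 1 trip in the baseline window and 6 in the week 24 window, it is (6 − 1) × £4.50 = £22.50. With the numbers reversed it is −£22.50. The mileage cells are the same at both visits, so they show no change in either case.

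**Step 3: can another part of the form supply n?** Appendix B does hold three-month counts:
- Outpatient: "Total number of appointments in last 3 months", by type of service.
- Inpatient: "Total number of admissions in last 3 months", by type of ward.
- Primary and community care: contacts, by type of service.
- Other costs: purchases and private visits together.

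These can serve as a rough multiplier, with four weaknesses:
- Travel rows are indexed by free-text location and the counts by service. No section links the two.
- No count row names IAPT, CBT or a psychological wellbeing practitioner. Therapy sessions would have to go under the psychologist row or under other.
- Some contacts need no journey; GP home visits have their own row. One journey can also serve several contacts.
- Section 5 describes the service's routine facilities as a GP clinic room or community venue. A location entered as a GP surgery could therefore mean a GP appointment or a therapy session.

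**The case against.** The strongest reply is that the information is largely there. The research nurse administers the form (section 7.4), can name the service in the location cell, and collects contact counts in the same interview. Pre-specifying how locations map to those counts, and a mileage rate, would fill much of the gap without touching the form. This stands in part. It rules out the reading that travel cost cannot be totalled at all: parking is already a total, and fares and mileage can be approximated. It does not make the approximation reliable, because the mapping is unstated and the therapy sessions have no named row.

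A second reply is that the same form is used at baseline, so any undercount affects both ends of the change. That is fair against a fixed percentage loss, but it does not make the error cancel. As Step 2 shows, the error in the change depends on how the number of trips differs between the two windows.

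A third reply is that the sums are small. Ten trips at £4.50 are £45, and £45 ÷ £2,895 (the cost of high-intensity therapy per participant in section 11.1) is about 1.6%. Using the £10 reimbursement cap in section 7.3 as a cost per trip, ten trips are £100, or about 3.5%. These figures rest on an assumed trip length and number, and they set a patient cost against an NHS cost. They suggest a modest scale but do not establish one. Travel also sits beside time off work, private purchases, additional care and informal care within the CSRI.

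**Conclusion.** The point holds in a limited form. The travel table lacks the trip count that its unit costs need, so three-month fares and mileage can only be estimated through an unstated link to service counts. A change in the number of trips to the same venue is invisible in the table. The effect is confined to the travel component of patient cost in the secondary objective. Its size is not known from the documents. The GAD-7 outcome and the sample size are untouched.

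Three stronger readings are tempting but not supported:
- A reader might infer that the form captures one trip in k, for example one of three (33%) for an assessment plus two sessions, or one of ten (10%) if ten trips are assumed. That holds only if the rows are added without a multiplier. No section plans this, and the ratios do not describe a change from baseline.
- A reader might infer that half of the secondary objective is at risk because patient cost is one of two costs named. The documents give no such weighting, and section 3.5 also measures that objective by EQ-5D-5L and WASA.
- A reader might infer that one trip's fare is certainly being mixed with three months of parking. The parking column states no period, so it is ambiguous rather than shown to be inconsistent.

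**What to change.** Add a column to the travel table for the number of return trips in the last three months, and state that parking covers the same three months. Compute travel cost as trips × (fare, or miles × a mileage rate fixed in advance) + total parking. A pre-printed first row for the IAPT venue is optional.

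The cost is one more question per location at each CSRI visit: with six rows and three visits, at most 6 × 3 = 18 extra entries per participant. It is best done before the form is used, because trip counts are hard to recover once the three-month recall period has passed.

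If forms are already in use, pre-specify how each location is matched to the outpatient, inpatient, community and private-visit counts. Say which contacts count as journeys and where IAPT sessions are recorded, fix the mileage rate, and report the travel estimate as approximate.
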